## AMENDMENT HISTORY

| Amendment No. | Protocol Version No. | Date issued | Author(s) of changes | Details of Changes made  |
|---------------|----------------------|-------------|----------------------|--|
| 1             | 1.2                  | 29/9/17     | [name] (CI)        | Inclusion of pregnancy test where appropriate, requested by MHRA |
|               |                      |             |                      |  |

## PROTOCOL SYNOPSIS

|                                     |   |
|-------------------------------------|---|
| Title                               | Pharmacokinetics of Intramuscular Adrenaline in Food-Allergic Teenagers - does dose matter?   |
| Abbreviated title                   | PIMAT study   |
| Eudra CT registration no.           | 2017-003239-13  |
| IRAS Identifier                     | 232931  |
| REC Number                          | 17/LO/1568  |
| Sponsor R&D Number                  | 17SM4137  |
| Clinicaltrials.gov registration no. | NCTxxx  |
| Primary objective                   | To assess the pharmacokinetics (plasma catecholamine levels) and pharmacodynamics (cardiovascular parameters) following intramuscular self-injection of 300mcg and 500mcg adrenaline using an auto-injector device, in food-allergic teenagers over 40kg.   |
| Secondary objectives                | To assess: 

1. The pharmacokinetics/pharmacodynamics following intramuscular self-injection of 300mcg adrenaline using different needle lengths (15mm vs 23mm).

2. The impact of self-administration of adrenaline autoinjectors (in a non-reaction setting) on health-related quality of life (HRQL) measures in food-allergic teenagers and their parents.

   |
| Study design                        | Open label, randomised cross-over interventional PK/PD study  |
| Patient group                       | Young people (13-18 years) of body weight over 40kg and prescribed an adrenaline autoinjector due to a diagnosis of IgE-mediated food allergy. Target recruitment: 12 subjects.   |
| Intervention                        | Intramuscular self-injection of adrenaline (using an autoinjector device) on 2 separate days, at least one month apart. The order of injections (300mcg vs 500mcg) will be randomised.  |
| Study outcomes                      | 
Primary Outcome:
 

• Plasma catecholamine profile following intramuscular injection of 300mcg vs 500mcg adrenaline.

 
Secondary Outcomes:
 

1) Change in cardiovascular parameters (HR/BP/SV) and adverse events following IM injection of 300mcg vs 500mcg adrenaline.

2) Plasma catecholamine levels and change in HR/BP/SV for 3 hours following IM injection of 300mcg using 2 different autoinjector devices with different needle lengths.

3) Change in HRQL measures 1 month following self-injection.

 |
| Safety                              | Patient screening to exclude relevant co-morbidities. Study interventions will be conducted on a paediatric research unit with continuous non-invasive cardiovascular monitoring, and overseen by trained clinical staff.   |
| Sponsor                             | Imperial College London   |
| Funding                             | Medical Research Council award to [name] (reference MR/K010468/1)   |

## Funding

Funding has been obtained from a Medical Research Council grant (reference MR/K010468/1) to [name].

This protocol describes the PIMAT study and provides information about procedures for entering participants. The protocol should not be used as a guide for the treatment of other participants; every care was taken in its drafting, but corrections or amendments may be necessary.

Problems relating to this trial should be referred, in the first instance, to the study centre.

This trial will adhere to the principles outlined in the Medicines for Human Use (Clinical Trials) Regulations 2004 (SI 2004/1031), amended regulations (SI 2006/1928) and the International Conference on Harmonisation Good Clinical Practice (ICH GCP) guidelines. It will be conducted in compliance with the protocol, the Data Protection Act and other regulatory requirements as appropriate.

## GLOSSARY OF ABBREVIATIONS

| ABBREVIATION | TERM   |
|--------------|--|
| AAI          | Adrenaline Auto Injector device  |
| ADR          | Adrenaline   |
| AE           | Adverse Event  |
| AUC          | Area under the curve. Derived from the drug concentration-time curve.                  |
| BP           | Blood pressure   |
| $C_{\max}$   | The post-dosing peak plasma concentration of a drug                                    |
| FAIM         | Food Allergy Independent Measure   |
| FAQL-Q       | Food Allergy Quality of Life - Questionnaire   |
| HR           | Heart rate   |
| HRQL         | Health Related Quality of Life   |
| IM           | Intramuscular  |
| PPI          | Patient and Public Involvement   |
| SAE          | Serious adverse event  |
| SAR          | Serious adverse reaction   |
| STMD         | Skin to Muscle Depth   |
| SV           | Stroke volume  |
| $T_{\max}$   | The time (in seconds) to reach $C_{\max}$  |
| $T_{1/2}$    | The time (in seconds) for the drug plasma concentration to reach half it's peak value. |
| USS          | Ultrasound   |

## 1. INTRODUCTION

### 1.1 BACKGROUND

Food allergy affects up to 2% of adults and 6% of children in the UK; it is the most common cause of life-threatening allergic reactions (anaphylaxis). Food allergy is a major public health issue, with practical implications for the food industry, educational establishments and healthcare systems. The risk of fatal food-induced anaphylaxis is very low but also unpredictable; this contributes to social restrictions and anxiety which result in the adverse impact of food allergy being comparable to that seen with other chronic illnesses, such as diabetes. Although death from anaphylaxis is rare, the risk is greatest for those aged 10-24 years.

A key management strategy is the provision of adrenaline autoinjector devices (AAIs) to those individuals at risk of anaphylaxis. The prescription of AAIs in the UK has more than doubled in the last decade. Prompt administration of intramuscular (IM) adrenaline is the recommended first-line treatment for anaphylaxis: adrenaline results in increased cardiac output, bronchodilatation and stabilization of mast cells and other effector cells, which counteract the effects of the allergic reaction.

Currently, three different AAIs are marketed in the UK and EU, available in a variety of doses (table 1). National recommendations on prescribing AAIs vary by weight and age, resulting in significant differences in practice amongst clinicians, and leaving a grey area for dosing in adolescents/adults weighing >30kg.

| Device                           | Mechanism                          | Doses   | Needle length | Needle gauge | Retractable or shielded needle | Shelf life | Distributor               |
|----------------------------------|------------------------------------|---------|---------------|--------------|--------------------------------|------------|---------------------------|
| EpiPen                           | Cartridge                          | 0.3 mg  | 15 mm         | 21           | Yes (shield)                   | 18 months* | Meda Pharmaceuticals Ltd. |
| EpiPen Junior                    |                                    | 0.15 mg | 13 mm         | 21           |                                |            |                           |

A single injection of adrenaline may be insufficient to counteract anaphylaxis: up to 20% of individuals experiencing anaphylaxis require a second dose of IM adrenaline to treat an accidental reaction, and one third of food-induced fatal anaphylaxis cases occur despite timely adrenaline administration. In an ongoing study, we have observed that teenagers may have anaphylaxis which does not respond to a 300mcg dose of self-injected adrenaline, but subsequent episodes respond well to a 500mcg dose (the BOPI study, NCT02149719, IRAS ID 158693). Given that the recommended dose of IM adrenaline for anaphylaxis is 500mcg, these observations imply that for teenagers and adults, using an AAI which only delivers 300mcg may undertreat the reaction and place such individuals at higher risk of severe anaphylaxis.

This concern was highlighted following the death of a teenager in 2010, which on the recommendation of the coroner prompted a review by the MHRA in 2014 into the clinical and quality considerations of AAIs. One recommendation in the MHRA report was that manufacturers 'should be encouraged to develop a 0.5mg [dose] AAI.' Currently, in the UK, only Emerade produces a 500mcg device.

Both the Coroner and MHRA also raised a further concern relating to needle length. As can be seen from Table 1, the current devices have varying needle lengths. In many children, particularly older females, the skin-to-muscle depth (STMD) is greater than the needle length of the AAI, which may result in a subcutaneous rather than intramuscular injection. There are limited data relating to the pharmacokinetics of IM adrenaline in young people and adults, with interpretation of findings being hampered by limitations in study design/sample choice. Simons et al demonstrated that IM (in contrast to subcutaneous) injection of adrenaline into the thigh results in a higher and faster peak plasma adrenaline level in children (Figure 1). Together with anecdotal data that subcutaneous adrenaline results in a slower clinical response, international guidelines for anaphylaxis management recommend the intramuscular route as the recommended route of administration. Importantly, no serious adverse events were reported in this and other studies of intramuscular adrenaline injection in healthy children and adults, although mild adverse events included tremor, palpitations and nausea.

[figure not shown]

FIG. 1. Mean plasma epinephrine concentration versus time plot after injection of epinephrine subcutaneously in nine children and after injection of epinephrine intramuscularly in eight children.

Medications and Healthcare Products Regulatory Agency. Adrenaline auto-injectors MHRA. a review of clinical and quality considerations. 04 June 2014. Available at: <http://www.mhra.gov.uk/home/groups/comms-ic/documents/websiteresources/con423091.pdf>

Recent data has highlighted that a 15mm needle length may be inadequate to deliver an intramuscular injection in up to 20% of adults (majority female) and up to one third of children. The situation may be worse in adolescents: in a UK-based study, over 61% of children weighing >30 kg had a proximal thigh STMD greater than 15mm. This was not limited to overweight/obese children: 25% of children of a healthy weight had a STMD greater than 15mm.

Although compression of the subcutaneous tissues during AAI administration might reduce the STMD, the degree of compression only results in a reduction of 0-1.2mm (interquartile range) and a subsequent study found that unless the deep muscle fascia is breached by the needle, the fascia forms an impenetrable barrier to fluid injected subcutaneously by autoinjectors irrespective of the propulsive force behind the injection. It is therefore not surprising that the MRHA report recommended that “the needle length for all AAIs should be reviewed by the manufacturers and increased, if necessary, to ensure that an intramuscular injection is delivered to a greater proportion of patients”. The MHRA also highlighted that further pharmacokinetic studies are needed to assess the impact of needle length on adrenaline absorption.

## 1.2 STUDY RATIONALE & JUSTIFICATION

The MHRA has highlighted the need for further in-human data relating to both dose and needle length in the AAIs prescribed to young people at risk of anaphylaxis, with a particular focus on obtaining pharmacokinetic data. Teenagers and young people are most at risk of fatal food-induced anaphylaxis, and are less likely than other ages to use their AAI.

We wish to formally assess the pharmacokinetics (PK) and pharmacodynamics (PD) of self-injection with intramuscular adrenaline in teenagers who are at risk of anaphylaxis due to food allergy, and have been prescribed AAI.

1. We will compare self-injection with 300mcg vs 500mcg in teenagers of body weight >40kg. We have chosen this weight cut-off as our local Network guidance is to consider switching teenagers over to a 500mcg device from 40-45kg. It should be noted that in a 40kg person, an adrenaline dose of 300mcg results in an effective UNDER-dosing of 30% by body weight.
2. We will also assess the impact of needle length on injection, by comparing two different devices, both of which deliver 300mcg, but one via a 15mm needle and the other with a 23mm needle.

Importantly, and in contrast to previous studies in young people, we will use a randomized-block crossover study such that each participant acts as their own control. This will increase the power of the study, controlling for differences in inter-person variation in adrenaline absorption. By undertaking the study in food-allergic teenagers, we are able to assess the PK and PD in individuals who are at greatest risk of fatal food-induced anaphylaxis, and provide training and supervision to them in the self-administration of AAI, something we have previously demonstrated increases self-efficacy and reduces the adverse impact on HRQL in such individuals.

Our study protocol and information sheets have been developed in consultation with food-allergic teenagers who have participated in previous studies on our research unit. We have specifically asked as to the perceived burden of the proposed interventions and have been reassured that the procedures proposed would not, in their opinion, be a barrier to their participation.

## 2. STUDY OBJECTIVES

### 2.1 PRIMARY OBJECTIVE

- To assess the pharmacokinetics (plasma catecholamine levels) and pharmacodynamics (cardiovascular parameters) following intramuscular self-injection of 300mcg and 500mcg adrenaline using an auto-injector device, in food-allergic teenagers over 40kg.

### 2.2 SECONDARY OBJECTIVES

To assess:

- 1) The pharmacokinetics/pharmacodynamics following intramuscular self-injection of 300mcg using different needle lengths (15mm vs 23mm).
- 2) The impact of in-hospital self-administration of adrenaline autoinjectors, in a non-reaction setting, on health-related quality of life (HRQL) measures in food-allergic teenagers and their parents.

### 2.3 STUDY HYPOTHESES

- 1) In young people over 40kg, intramuscular self-injection of 500mcg adrenaline results in a greater peak plasma adrenaline level compared to 300mcg injection, without causing a significant increase in adverse events.
- 2) In young people over 40kg, self-injection using an AAI with a 23mm needle will result in a more-favourable PK profile than an alternative device with a 15mm needle, without causing a significant increase in adverse events.
- 3) Self-administration of AAI as a method to provide training in the use of AAI is associated with a positive impact of HRQL measures in food-allergic teenagers.

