### 3. STUDY DESIGN

**Type of Study:** Open label, randomised cross-over study at a single centre.

**Number of Subjects:** 12 children will be recruited from the Adolescent Allergy Service at St Mary's Hospital, Paddington.

**Expected Duration:** Recruitment to commence 1st September 2017

Two clinical visits (full day) one month apart, with a follow-up questionnaire one month after the second visit.

Expected completion: 31 July 2018.

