## 9. STATISTICS AND DATA ANALYSIS

### 9.1 SAMPLE SIZE ESTIMATION

This is an exploratory analysis to assess the pharmacokinetics/pharmacodynamics of self-injection of adrenaline in young people with IgE-mediated food allergy. Existing PK/PD studies have not, in general, used a crossover design, but a parallel design with sample size from 5-9 participants per study arm.

In this study, with a cross-over design and a sample size of 12, we expect to detect, with 80% power, a treatment difference of 0.35pg/ml at a two-sided 0.05 significance level (this is based on pilot data (n=55) where the standard deviation of the difference between baseline plasma adrenaline levels on 2 separate occasions in the same individuals was 0.39 pg/ml). In a previous parallel-design study comparing EpiPen 0.15mg to 0.3mg, the latter dose was associated with plasma levels of, on average, >500pg/ml. We therefore expect a sample size of 12 should provide sufficient power to detect any difference in plasma catecholamine levels following AAI administration due to differences in dose or needle length.

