### 9.2 SIGNIFICANCE LEVEL AND CONFIDENCE INTERVALS

95% confidence intervals will be reported. Where comparisons are made between sub-groups a 5% significance level will be used.

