### 9.3 ANALYSES

Descriptive tables of numbers by age, gender, baseline variables and adverse events following AAI administration will be produced.

Paired data will be analysed, according to the paired difference between outcomes within the same individual between the different interventions, with all comparisons to data arising from Emerade 300mcg intervention. The planned analyses will therefore be:

- 1) Difference in peak plasma epinephrine ( $C_{max}$ ), time to  $C_{max}$  ( $T_{max}$ ), area under the plasma epinephrine versus time curve (AUC) between Emerade 300mcg and Emerade 500mcg.
- 2) Difference in peak plasma epinephrine ( $C_{max}$ ), time to  $C_{max}$  ( $T_{max}$ ), area under the plasma epinephrine versus time curve (AUC) between Emerade 300mcg (23mm needle) and Epipen 0.3mg (15mm needle).
- 3) Blood pressure, heart rate, stroke volume and change in PEFR versus plasma epinephrine concentrations over time after AAI administration (compared to both baseline and to Emerade 300mcg) will be explored using analysis of variance, analysis of covariance, and linear regression analyses.
- 4) Change in HRQL measures (FAQLQ, FAIM, self-efficacy) 1 month following each study visit, compared to baseline.

Other exploratory analyses:

- 1) Pharmacokinetic parameters of IM adrenaline injection ( $T_{1/2}$ , terminal elimination half-life;  $Cl$ , total body clearance;  $Vdss$ , volume of distribution at steady state) will be calculated from plasma epinephrine concentration versus time plots using Prism.
- 2) For the comparison between Emerade 300mcg (23mm needle) and Epipen 0.3mg (15mm needle), a sub-analysis of the difference in  $C_{max}$ ,  $T_{max}$  and AUC will be undertaken with reference to body weight, BMI and STMD.

Statistical differences will be determined using paired T-test for parametric data, or Wilcoxon signed-rank test for non-parametric data.

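### The safety clause in hypotheses 1 and 2 has no decision rule, and with 12 pairs the absence of a significant increase in adverse events cannot support a no-increase conclusion

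*Combined protocol and SAP*

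**What the plan says.** Section 2.3 pairs a pharmacokinetic claim with a safety claim in two of its three hypotheses: 500mcg against 300mcg, and the 23mm against the 15mm needle, each "without causing a significant increase in adverse events". The word significant is not defined as statistical or clinical.

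AEs are a secondary outcome (3.1.2, item 3). The synopsis presents them as a comparison: "adverse events following IM injection of 300mcg vs 500mcg adrenaline".

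Section 3 sets the size: "12 children will be recruited from the Adolescent Allergy Service". The only power statement, in 9.1, concerns plasma adrenaline: "we expect to detect, with 80% power, a treatment difference of 0.35pg/ml", "at a two-sided 0.05 significance level". The same section calls the study exploratory.

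For AEs, 9.3 Analyses says: "Descriptive tables of numbers by age, gender, baseline variables and adverse events following AAI administration will be produced". It does not say the tables will be split by device. The four planned analyses that follow cover pharmacokinetic parameters (two contrasts against Emerade 300mcg), cardiovascular and peak-flow data, and quality of life. None covers AEs. The tests named at the end of 9.3 are the paired t-test and the Wilcoxon signed-rank test.

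The section on significance level and confidence intervals promises 95% intervals in general terms and adds: "Where comparisons are made between sub-groups a 5% significance level will be used".

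**The concern.** A hypothesis that something does not increase needs either a margin that the data can exclude or an interval for the reader to judge. This one has neither attached to it. If the results are set against section 2.3 as written, the safety half can be called supported because no increase reached significance in a test nobody planned, or because a descriptive table looked unremarkable. Neither shows that AEs did not rise.

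Section 1.2 says local guidance already considers moving teenagers to a 500mcg device from 40-45kg, and 1.1 cites the regulator's interest in a 0.5mg device and in needle length. A published statement that the higher dose or longer needle brought no significant increase in AEs would enter that discussion, although the data could not exclude a large increase.

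**Working it through.** **Inputs from the documents.** n = 12 in a crossover, so at most 12 pairs per comparison (section 3). Two-sided significance level 0.05 and 80% power (9.1). For adrenaline, a difference of 0.35 pg/ml, where "the standard deviation of the difference between baseline plasma adrenaline levels on 2 separate occasions in the same individuals was 0.39 pg/ml" (9.1).

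**Inputs assumed.** AE rates per device. Section 1.1 says only that mild events such as tremor, palpitations and nausea occurred in earlier studies. The test is also assumed: an exact two-sided McNemar test on whether a participant had any AE.

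**Step 1. The plan's own figure.** Normal formula: n = (SD × (1.960 + 0.842) / difference)² = (0.39 × 2.802 / 0.35)² = 9.7, so 10. With the noncentral t distribution at n = 12, power is 80.8% on 11 degrees of freedom and 80.0% on 10. The detectable difference is 0.347 or 0.350 pg/ml. The stated figure reproduces from its own inputs, but it has no bearing on AEs.

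**Step 2. What 12 pairs need for significance.** Only discordant pairs (an AE on one intervention and not the other) carry information. If all m discordant pairs go one way, p = 2 × 0.5^m:
- m = 5: p = 0.0625
- m = 6: p = 0.031

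So at least six of the 12 participants must be discordant and, if exactly six, all in the same direction.

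**Step 3. Chance of declaring a significant increase.** Let p1 be the reference rate and p2 the comparator rate. With independent responses, the probability of an AE on the comparator only is p2(1 − p1), and on the reference only p1(1 − p2). With nested responses (everyone with an AE on the reference also has one on the comparator), these are p2 − p1 and 0. Summing exact binomial probabilities over all outcomes:

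| True rates | Detected, independent | Detected, nested | Missed |
|---|---|---|---|
| 20% to 40% | 5.8% | 1.9% | 94-98% |
| 25% to 50% | 9.9% | 5.4% | 90-95% |
| 20% to 50% | 15.1% | 11.8% | 85-88% |
| 20% to 60% | 30.2% | 33.5% | 67-70% |
| 20% to 70% | 50.2% | 61.3% | 39-50% |
| 20% to 80% | 71.8% | 84.2% | 16-28% |
| 10% to 70% | 74.4% | 84.2% | 16-26% |

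In the nested case, 80% power needs a rise of about 58 percentage points. A one-sided test with independent responses helps little: 11-12% detection for 20-point rises (10% to 30%, 20% to 40%) and 25-27% for 30-point rises (10% to 40%, 20% to 50%, 30% to 60%).

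**Step 4. Zero events.** If an event is seen in 0 of 12, the upper two-sided 95% limit for its rate is 1 − 0.025^(1/12) = 0.265, about 26%.

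**Step 5. A margin instead.** Assume 30% discordance and no true difference. The approximate 95% half-width is 1.96 × √(0.3/12) = 0.31. A non-inferiority reading has 80% power (one-sided 0.025) only for a margin of 2.802 × √(0.3/12) = 0.44. A 20-point margin would need 2.802² × 0.3 / 0.20² = 58.9, so about 59 pairs.

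**The case against.** The strongest reply is that the plan never proposes to test AEs. Significant may mean clinically significant, the McNemar test is not in the document, and descriptive AE reporting is a reasonable choice for an exploratory Phase IV study of 12 people. The power claim is confined to plasma catecholamines, and participant safety does not rest on the clause: AEs are graded and attributed (7.2), and a serious adverse reaction puts the study on hold (7.4). The promise of 95% intervals is also general and does not exclude AEs.

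Most of this stands, and it rules out two stronger readings. A reader might infer that the sponsor plans to take a non-significant AE test as proof of safety. No section says so, and no such test is specified. A reader might also infer that the clause would be met almost whatever the truth. That is too strong, since detection reaches 50-61% for 20% to 70% and 74-84% for 10% to 70%.

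Two further limits apply. The rates are assumptions, and if mild effects are common, any-AE rates could sit near their ceiling. The calculation also reduces AEs to yes or no, although 7.2 grades them from 1 to 5, so the miss rates apply only to that form of outcome.

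None of this rescues the clause. If significant means clinical, no clinical threshold is given. If it means statistical, no contrast or test is given, and the general promise of intervals has no AE contrast to attach to. Calling the study exploratory is a reason to estimate a difference, not to hypothesise that there is none.

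**Conclusion.** The point holds as a defect in the hypotheses and the AE analysis, not in the sample size calculation. Section 2.3 states a safety conclusion for which the plan gives no margin, power, test or between-device contrast, and 12 pairs could not support it through non-significance. Under the assumed rates and the illustrative test, true rises of 20, 30 and 40 points from a 20% base would be missed about 94-98%, 85-88% and 67-70% of the time. Detection becomes likely only for rises of about 60 points. The documents do not support reading this as a planned inference from a failed test, or as insensitivity to every possible increase. It should be corrected, because the wording decides what the trial may claim about dose and needle length, and the correction needs no extra participants or visits.

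**What to change.** 1. **Section 2.3.** Delete the safety clause from hypotheses 1 and 2.
2. **Section 2.2.** Add a secondary objective: *to estimate the within-person difference in the proportion of participants with any AE, and with any grade 2 or higher AE, between interventions.*
3. **Section 9.3 Analyses.** Report AE proportions per device, and the paired difference with an exact 95% confidence interval, for Emerade 500mcg versus Emerade 300mcg and for EpiPen 0.3mg versus Emerade 300mcg. Name the interval method and confirm that the planned software provides it.
4. **Observation window.** For the comparison, count only AEs with onset in the same window after each injection, for example the 3-hour monitored period, which ends before the second dose on the two-dose day. List later AEs separately. This is needed because the two 300mcg doses are given 4 hours apart on one day (section 6). An AE reported at the next-day call may not be attributable to one device, and a per-visit count would set 2 × 300 = 600mcg against 500mcg.
5. **Interpretation.** State that non-significance will not be read as no increase.

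The cost is revised wording in 2.2 and 2.3, a short addition to 9.3 with the window rule, and AE onset times recorded well enough to apply it. The price is a more cautious safety conclusion with wide intervals, roughly ±31 points at 30% discordance.
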